We may enroll a small group (n=30) of listeners with normal hearing, defined as pure-tone thresholds of 25 dB HL or less at octave frequencies between 250 and 3000 Hz. This group may be enrolled for the purposes of test validation, or to study the effects of hearing loss on the outcome measures. With the exception of having normal hearing, those participants will follow the inclusion and exclusion criteria described above.

The study will not recruit special populations such as adults unable to consent/cognitively impaired, minors, prisoners, or other detained individuals.

4.0 Sample Size:

The study will recruit 120 participants over a 3-year period. Each experiment will recruit approximately 30 participants (additional 10 account for pilot testing and attrition) for a total of 3 experiments.

Sample size considerations were based on the primary analyses of a mixed effect model with fixed effects for WDRC, working memory, and the interaction.

Simulations were performed based on a range of effect sizes and estimates of between subject and within subject variances. Our sample size of 15 subjects per working memory (high vs low), will provide at least 80% power to detect reasonable effect sizes for all three effects. Specifically, we assumed a conservative subject variance estimate of 0.01 and a residual variance estimate of 0.01 from pilot data, marginal effects for working memory of 0.70 (high) and 0.53 (low), and marginal effects for WDRC of 0.75 (fast) and 0.48 (slow). In simulations assuming a two-sided type one error, we had adequate power to detect all three effects. In simulations assuming less conservative variance estimates, our sample size will provide adequate power to detect even smaller effect sizes. Specifically, we assumed a subject variance estimate of 0.008 and a residual variance estimate of 0.006, marginal effects for working memory of 0.38 (high) and 0.17 (low), and marginal effects for WDRC of 0.33 (fast) and 0.22 (slow). We anticipate a range of effect sizes and variance estimates for models within each level of directionality, and thus considered simulations from a range of assumptions.

5.0 Recruitment and Screening Methods:

Recruitment process:

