The proposed study will recruit 120 adults (18 years or older) over a three year period. Participants will be primarily recruited from an existing database in the lab that has over 300 adults with hearing loss who are interested in study participation and agreed to be contacted for future research. The lab also has access to a Communication Research Registry, a confidential database for individuals interested in continuing research participation within the Northwestern School of Communication. Additional recruitment will take place through the department's audiology clinic, local senior centers, and local Hearing Loss Association of America (HLAA) chapter using flyers. Recruitment flyers will also be disseminated through flyers on bulletin boards throughout the Northwestern campus. Advertisements will be posted in local boards. Interested participants will be contacted by the research staff via phone or email as preferred by the potential participant. At this time, the participant will be provided basic information regarding study procedures and inclusion criteria.

Screening process:

Prior to enrollment in the study, potential participants will go through a screening process. The screening procedure will take approximately 60-80 minutes. The following tests may be conducted to verify eligibility for research inclusion:

Test	Description/Purpose	Exclusion Criteria
Case history	Written administration; questions re: onset/nature of hearing loss, hearing aid use, otologic and medical history; CEDRA questionnaire [21]	Significant history of otologic/neurologic disorders
Otoscopy	Visual examination of pinna, ear canal, and ear drum	Significant impaction of wax, active discharge; exclusion will be determined in

		conjunction with tympanometry when appropriate
Tympanometry	Test to determine middle ear status	B-type tympanogram suggesting unhealthy middle ear status
Audiogram*	Air conduction (250 Hz to 8000 Hz) and bone conduction (500 Hz to 4000 Hz) testing to determine degree and type of hearing loss	Evidence of conductive hearing loss (air-bone gap > 10 dB HL); Hearing loss > 70 dB HL at any frequency between 250-3000 Hz; Evidence of significant asymmetry between ears (≥ 15 dB HL at 3 or more frequencies OR ≥ 20 dB HL at any 2 frequencies) [14]
Monosyllabic word recognition	Percentage of phonetically-balanced words repeated in quiet at a comfortable loudness.	Evidence of significant asymmetry between ears [15]

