Due to the COVID-19 pandemic, participant research visits may be conducted remotely using Northwestern IT-approved (and HIPAA-approved) video conferencing or phone. The research staff will conduct these visits from a private room in their apartment and no one else will be present during the research study. The research staff may also conduct these virtual visits from the hearing aid lab or an office space. Participants will perform the remote testing from their respective places of residence/a quiet place of their convenience. The virtual visits will be conducted either through Zoom or Microsoft Teams or WebEx applications. The platform used will be determined by participant preference.

7.0 Multi-site Research (research that involves external collaborating institutions and individuals): N/A

8.0 International Research (where data collection will occur outside the United States and U.S. territories): N/A

9.0 Procedures Involved:

The proposed research will measure speech intelligibility and signal fidelity with a combination of hearing aid settings under a variety of spatial conditions (Aim 1: ideal; Aim 2: realistic) for hearing-impaired listeners with different working memory capacities. The proposed research is a clinical trial and will use laboratory hearing aids to provide various combinations of hearing aid signal processing. Using a mixed design, individual variability in auditory and working memory capacity will be related to speech intelligibility and signal fidelity across test conditions. Test procedures including stimuli and outcome measures described below are common to both Aims 1 and 2.

Study tasks for all experiments will include the following steps per subject:

Session 1	Approx. Duration (2 hours)	Session 2	Approx. Duration (2 hours)	Session 3	Approx. Duration (2 hours)
Candidacy assessment	60-80 mins	Earmold + Hearing Aid Fitting	45-60 mins	Outcome measurement (Speech intelligibility testing, localization) continued	60-120 mins
Cognitive test*	15-30 mins	Outcome measurement (Speech intelligibility testing)	60 mins		
Earmold impression	15-20 mins				

*May include tests of working memory, executive function, and processing speed

Session 2 will take place ~10-15 days after session 1 to allow for time taken for the custom earmold order to be received. There is no minimum gap required between sessions 2 and 3. Session 3 may not be required for all experiments or participants.

Stimuli:

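### Section 4 sizes the primary interaction on high and low working memory groups although Reading Span is a numeric score, and the SAP states no coding; the score should be entered as measured, fixed before outcomes are seen

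*Protocol*

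**What the plan says.** Protocol Section 4 ties its sizing to the main analysis: "Sample size considerations were based on the primary analyses of a mixed effect model", with terms for WDRC, working memory and their interaction. It then codes working memory as two groups: "Our sample size of 15 subjects per working memory (high vs low"), and claims at least 80% power for all three effects. Two scenarios are given as marginal means only. For WDRC these are "marginal effects for WDRC of 0.75 (fast) and 0.48 (slow") and "marginal effects for WDRC of 0.33 (fast) and 0.22 (slow"). No interaction size is given.

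Section 9 measures working memory in every participant with the Reading Span test, scored by the number of words recalled. No cut is stated.

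Section 5 introduces its screening table with "The following tests may be conducted to verify eligibility for research inclusion"; Reading Span is not in the table. Cognitive testing is in Session 1, with the footnote "May include tests of working memory, executive function, and processing speed", and Session 2 follows about 10 to 15 days later. Section 9 also says: "Using a mixed design, individual variability in auditory and working memory capacity will be related to speech intelligibility and signal fidelity across test conditions".

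The SAP's primary question is whether the effect of hearing aid processing on percentage correct depends on working memory ability. Its linear mixed model has working memory, processing and their interaction as fixed effects. It does not say whether working memory is a group or a score, and does not name the test.

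**The concern.** The interaction is the primary question, so the coding of working memory defines the primary test. The one coding on paper turns a numeric score into two groups, with no rule for forming them. Two consequences follow.

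- Grouping a numeric score discards the differences between listeners within each half. When the trend is roughly linear, this costs power on the interaction.
- If the coding is still open once outcomes exist, two defensible tests of one hypothesis are available. A cut set from span scores alone does not bias the test. A sample median, however, is known only when the last listener has been tested, by which time earlier listeners may have outcomes. The rule therefore has to be written first.

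A secondary reporting point: marginal means do not determine an interaction, so a reader cannot check the power claim for the effect that matters most.

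**Working it through.** **Inputs.** From Section 4: 15 v 15; residual variance 0.01 or 0.006; subject variance 0.01 or 0.008; working memory means 0.70 v 0.53 and 0.38 v 0.17; WDRC means 0.75 v 0.48 and 0.33 v 0.22. About 30 listeners per experiment plus 10 for piloting and attrition gives 3 × 40 = 120, matching "The study will recruit 120 participants over a 3-year period". Assumed, because not stated: alpha 0.05 two-sided, one score per listener per WDRC level, score shape, and linearity.

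**1. Section 4's own figures (main effects).**
- Working memory, scenario 1: SD of a listener's mean = √(0.01 + 0.01/2) = 0.1225; SE = 0.1225 × √(2/15) = 0.0447; 0.17/0.0447 = 3.80; power 96% (t, 28 df).
- Working memory, scenario 2: SE = √(0.008 + 0.006/2) × √(2/15) = 0.0383; 0.21/0.0383 = 5.48; power >99.9%.
- WDRC: SE = √(2 × 0.01/30) = 0.0258, ratio 0.27/0.0258 = 10.5; and √(2 × 0.006/30) = 0.020, ratio 0.11/0.020 = 5.5; power >99.9% in both.

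The main-effect claims reproduce.

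**2. The interaction claim.** The subject effect cancels in each listener's fast-minus-slow difference, so the interaction test compares these differences between groups. SD = √(2 × 0.01) = 0.1414; SE = 0.1414 × √(2/15) = 0.0516. With no trend inside either group, 80% power needs a high-low gap of 0.150 (0.116 with residual variance 0.006). No gap is stated, so the claim can be neither confirmed nor refuted.

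**3. Information kept by a median split.** For a normal score, the squared correlation between score and group is 2/π = 0.64, so 30 split listeners are worth about 30 × 0.64 = 19 analysed on the score. Over five other score shapes the loss is 27% to 43%.

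**4. Power over interaction sizes.** Simulation: 30 unselected listeners, normal score, linear trend, residual variance 0.01, t test on 28 df. The gap is the difference in mean WDRC effect between the upper and lower halves, so slope per SD = gap / (2√(2/π)) = gap/1.596.

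| High-low gap | Slope per SD | Median split | Continuous |
|---|---|---|---|
| 0.12 | 0.075 | 55% | 77% |
| 0.15 | 0.094 | 72% | 91% |
| 0.20 | 0.125 | 90% | 99% |
| 0.27 | 0.169 | 98% | >99.9% |

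At residual variance 0.006 and gap 0.20 the figures are 98% v 99.9%. At gap 0.15 the split has 72% here, against 80% in step 2, because a linear trend leaves variation inside each group.

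**5. If listeners were selected on span.** With 15 from each outer third the loss falls to 18–19% (80% v 88%). With 15 from each outer quarter it is 12–13% (80% v 85%).

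**6. Coding chosen after outcomes.** If either the 15/15 split or the continuous score may be reported, a nominal 5% test rejects in about 8% of null trials (7.4–8.2% over score shapes; about 7% with outer thirds or quarters).

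**7. When the trend is not linear** (continuous v split, split calibrated to about 80%): flat above average 94%; gentle S-curve 89%; steep S-curve 79%; step at the population median 73%; step exactly at the sample split 57%.

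**The case against.** The strongest reply is that no passage commits the primary analysis to two groups. The high/low split appears only in the sizing paragraph, and Section 9's reference to individual variability suits a score at least as well. If the score is to be analysed as measured, a two-group calculation is merely conservative for unselected listeners with a linear trend. This stands, and it makes the power loss conditional. It does not remove the point: Section 4 says that its sizing follows the primary analyses, and nothing in the SAP replaces its coding.

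The loss also depends on the interaction. It is large at gaps of 0.12 to 0.15 and nearly gone at 0.27. Several scores per WDRC level, which Section 9's varying babble levels would allow, would raise power under both codings. And a cut fixed in advance would protect the false-positive rate just as well. All of this stands: prespecification is the essential part, and the continuous score is the more efficient default.

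Three stronger readings are tempting and not supported:
- A reader might infer that the analyst may try any cut; allowing every cut from 10/20 to 20/10 would give about 18% false positives. Section 4 fixes 15 per group, so unequal cuts do not fit it. Nor does any passage say that the choice will be made after outcomes are seen.
- A reader might compare the detectable gap of 0.116 with the second scenario's WDRC effect of 0.11 and conclude that the trial cannot detect its interaction. That gap assumes no trend within groups and one score per level, and a main effect is no benchmark for an interaction.
- A reader might infer that Section 4's power is wrong. Its main-effect figures reproduce.

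**Conclusion.** The point holds as a cheap improvement, not as an error in a stated result. The only coding on record is two groups of 15 made from a numeric score, and the SAP neither adopts nor replaces it. If unselected listeners are split at the median, about 36% of the information on the primary interaction is lost; at residual variance 0.01 this is some 19 to 22 points of power at gaps of 0.12 to 0.15, 9 points at 0.20, and little at 0.27. If the choice between that split and the continuous score waited for outcomes, the 5% test would run at about 8%. These sizes rest on a normal score, a linear trend, one score per WDRC level and alpha 0.05; selection from the extremes, which no passage describes, would shrink the loss. The unstated interaction size is a secondary reporting gap under either coding.

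**What to change.** State in the SAP, before outcomes are seen, that the primary model enters the Reading Span score as a continuous centred covariate with its interaction with processing. Name the test, since Section 9 also describes a divided-attention task that yields a working memory span. Use high and low groups for display and sensitivity analysis only, under a rule fixed in advance. Re-run the Section 4 simulation under that model and state the interaction size and alpha assumed. If groups are truly intended for the primary analysis, fix the cut and how 15 per group is reached before outcomes are seen. Session 1 testing makes early fixing feasible.

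The cost is wording in two documents and a re-run simulation; no added participants or visits. The downside is a linearity assumption that 30 listeners can check only roughly, and lower power than the split if the true relation is a step. The grouped sensitivity analysis covers that case.

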10.0 Research with Vulnerable Populations: N/A

11.0 Incomplete Disclosure or Deception: N/A

12.0 Consent Process:

Prior to enrollment in the study, potential participants will have a hearing, vision, and cognitive test with authorization by a screening consent form. These tests will allow us to exclude potential participants who are ineligible based on their hearing, vision, or cognitive status from enrolling in the study. These tests will be built into the first visit tasks and will last 60-80 minutes. If the participant is eligible based on the screening process, he/she will be consented for the experimental procedures using a separate form. If a participant is not eligible based on screening, they will have the option to authorize future contact and authorize the lab to retain the screening audiogram and cognitive test results. Consenting will take place in the Hearing Aid Lab, prior to any research procedure taking place. All consent forms are stored in a locked file cabinet within the Hearing Aid lab (locked lab). The potential participant will be provided unlimited amount of time to review the consent forms and ask any clarifying questions. Following the participant's opportunity to review the consent form, the researcher will review each section with the participant to clarify any study procedure and ensure understanding. All participants will be offered a copy of their signed consent form with the option to decline. The researcher will document the consent process and the participants' receipt of/decline of a signed copy on a study flow sheet. Both participant and staff will initial the flow sheet to verify that the consent form was provided or that a copy was declined. Please note that during the consent process, the researcher will explain to the participant that their identifiable information will be kept confidential and will not be used.

Due to the COVID-19 pandemic, virtual consent will be obtained from any newly enrolled study participants in order to minimize risk of exposure. Participants will be consented using one of two procedures, determined by participant preference:

Option 1: The participant will be consented electronically using REDCap. The participant will be required to “sign” by typing their name and enter the date. The participant will be able to review the consent form as many times as they need to, go back and forth through sections, and take their time before providing their consent. They may save their progress on the form and return to it at a later time if needed. The participant may contact a study team member as needed to provide any clarifications regarding any part of the consent form via phone or email or video before the deciding to provide their consent. All information required for informed consent will be available on the eConsent forms. Consent forms for this study do not have any associated external material or hyperlinks. In order to ensure the identity of the signer, the REDCap consent form can only be accessed by the email address that it is sent to (i.e., the email address provided by the

participant). In addition, the participant will be provided with a predetermined passcode via phone or video. At the time of accessing the electronic consent form, the participant must enter the passcode which will be internally compared with the stored version entered by the study team member. The participant will be granted entry only if the passcode matches. The participant will have the option of saving a copy of their signed eConsent forms as PDFs. A study team member will review the submitted eConsent form and electronically sign and date as confirmation.

Option 2: The participant will be sent a consent form via encrypted email, which they will sign and date, scan/take a photo of, and email back to the research staff. The participant may contact a study member as needed to provide any clarifications regarding any part of the consent form via phone or email or video before the deciding to provide their consent. The staff member will review the submitted consent form and sign and date as confirmation. The participant will be sent a scanned copy of the signed consent form for their records.

13.0 Research with Children – Parental Permission, Child Assent, and Other Considerations: N/A

14.0 Waiver of Participant Signature on Consent Form: N/A

15.0 Waivers and Alterations of Consent Information: N/A

16.0 Financial Compensation:

Upon completion of the study tasks, the participant will be paid an hourly rate for participation (\$15/hour). Payment will be made in cash at the conclusion of each session. If the participant decides to withdraw from the study before its completion, he/she will be paid \$15/hour for the time spent. There is also dedicated parking space for research participants (at no charge) and an accessible entrance to the lab building.

Due to the COVID-19 pandemic, participants will be given the option of being compensated at the above rate in the form of a Hyperwallet Virtual Card provided by Northwestern University in order to minimize the risk of exposure. The card will be issued at the completion of the study visit at which point the participant will be emailed instructions for the card activation process. For participants who do not have access to email, they will also be given the option of being issued a check or a physical gift card for the amount that they are owed. Financial compensation will not be withheld in the event of loss or damage to any experimental equipment.

17.0 Audio/Video Recording/Photography

Audio and video recordings may be obtained during the screening tests and the listening tasks. The purpose of the audio/video recordings is to ensure accuracy (a second scorer may listen to the recordings and correct any potential errors). The recordings will contain only non-identifiable information and will be destroyed 3 years after the completion of the study. Audio and video recordings will not be obtained during earmold impressions and hearing aid fitting.

18.0 Potential Benefits of this Research:

Participants in this study may not directly benefit from the experiment. The findings from this research can result in improvements in clinical decision-making for hearing aid fittings and audiological care. Therefore, participants with hearing loss seeking hearing aids may benefit in the long-term. Many participants are interested in hearing aid research as an opportunity to get information and ask questions about hearing aids without sales pressure. All participants will have the opportunity to receive counseling at the end of the study, by the investigators or the research coordinator, all of whom are also trained and certified audiologists. Counseling, if and when provided, will include listening recommendations tailored to their individual speech understanding and memory. Participants will have the chance to ask questions and receive information about options for their hearing loss (outside the study).

19.0 Risks to Participants:

All study procedures pose minimal risk to participants. There is potential that the study task might be boring or repetitive, and therefore if a participant wishes to discontinue testing at any point, they may choose to do so without any consequence. Listeners who receive poor scores on the cognitive tests may be disappointed to learn of their performance. Some listeners may find the sounds processed through the hearing aid simulator to be sharp or tinny in comparison to their unaided hearing. These are normal and expected consequences of any hearing aid fitting. Loudness discomfort levels will be measured and presentation levels will be monitored to ensure that levels never become uncomfortable. When the earmold impression is taken, participants may experience some temporary discomfort or a ticklish feeling as the cotton/foam block is placed into the ear canal. Participants may also notice that the impression material is slightly cold, or experience a feeling of pressure while the impression material is in your ear. Rarely, there can be some minor abrasions to the skin of the ear canal. These procedures are routinely used when fitting hearing aids or creating custom earplugs and the risks in this study are no higher than the risks that would be experienced in an audiology clinic.

The hearing aids and earmolds will only be used for the duration of the experiment. The participant is free to remove the hearing aids and/or leave the test booth at any time. Participants are encouraged to take breaks and can discontinue the study at any time without penalty. If the investigator determines participation

in the study places a participant at unacceptable risk, enrollment or study tasks will not proceed.

Participant confidentiality will be ensured by storing data without subject identifiers. Data files are password protected and can only be accessed by authorized lab members. Hard copy data are stored in locked file cabinets within a restricted-access laboratory space. All study staff complete training in ethical procedures for working with human subjects and in HIPAA regulations.

If a research participant decides to withdraw or discontinue study procedures, all data collected up to that point can be used by the investigator unless the participant indicates that they would like to have their data removed from the study. In the event that a participant is removed from the study without their consent, compensation will be pro-rated based on the duration the participant remained compliant with study tasks and procedures.

In the event that a participant is compensated using the Hyperwallet Virtual Card, an account will need to be created using the participant's name and email address, which will link their name to the study. This creates a small additional risk of breach of confidentiality.

